7.2.7.1 Blinding Procedures

The clinical investigation is partially blinded, with the subject and delegated site personnel who will administer tests and subject facing questionnaires and program the device being blinded to the treatment assignment. This is to reduce risk of bias during these assessments. Training to blinding and unblinding procedures will be provided prior to site personnel prior to them completing clinical investigation activities. Where required for resourcing reasons, prior approval may be sought from the Sponsor for site personnel to be blinded to the subjects they will test, but not the subjects they will not test.

IMD and comparator packaging will be visually identical with exception of tracking numbers that will not identify the device type.

Investigators performing the cochlear implant surgery will not be blinded to the randomisation assignment. Blinding the surgeon is not possible as there are visually apparent differences between the two devices. Surgeons and other unblinded site personnel will be instructed to not disclose randomisation assignment through discussion, documentation or other means. The surgeon will be instructed to document the "cochlear implant" (or similar) was implanted in medical records. The monitor will need to ensure blinded site personnel do not become unblinded during discussions.

The Data Management Plan includes processes for managing the randomisation process. The Sponsor will not be blinded to the randomisation assignment. The Sponsor's delegated monitor(s) will be blinded to the randomisation assignment.

Investigators completing adverse event assessments will be blinded to the randomisation assignment. The IDMC will be aware which randomisation group a subject is randomised, but identification of the group (Cl632 or Cl632D) will not be provided to the IDMC. The Sponsor will only analyse data as outlined in this clinical investigation plan. The Sponsor will provide data to the IDMC as outlined in the IDMC Charter and as requested; the Sponsor will not evaluate this data.

At the end of the clinical investigation, the database will be locked. After this time point, subjects and blinded site-personnel may be unblinded to the randomisation assignment and subjects' medical records may be updated.

If a subject becomes unblinded or an unblinded site personnel completes assessments with subjects they are unblinded to, it must be recorded in the EDC as a protocol deviation. If site personnel become unblinded, efforts should be made to assign an alternative blinded site personnel to complete assessments with the subject. In the event blinding must be broken, the decision should be documented by the Principal Investigator and the Sponsor should be notified.

Designated Sponsor personnel will have access to the randomisation assignments. If unblinding is required, the site may contact the Sponsor to retrieve the subject's randomisation assignment.

7.2.8 Post-investigation Medical Care

Following the investigation, subjects will continue with standard of care treatment.

7.3 Evaluations and Procedures

For each enrolled subject, the clinical investigation will include Screening and Baseline procedures, Randomisation assignment to the IMD or comparator, Surgery to implant the assigned device, and seven postsurgical follow-up visits.

7.3.1 Screening/eligibility

Screening and Baseline may be completed in parallel. If historical exams are available, they must be within the timeframes indicated below. The following must be completed prior to Randomisation:

- Written informed consent: must be completed before any study specific procedures are completed.
- Demographics: document age and sex.
- Eligibility: confirm subject meets all inclusion criteria and no exclusion criteria (see section 7.2.1 and 7.2.2). Source documentation must be available before confirming eligibility.
- Hearing History: document history of hearing loss (may be subject reported)
- Device history: document history with hearing aids and cochlear implant (contralateral ear) (may be subject reported)
- Medical History: document medical history.

- Audiogram: must be completed less than 90 days prior to randomisation and document bilateral, moderate to profound hearing loss. (see section 7.3.2.2)
- Speech Perception testing: must be completed less than 90 days prior to randomisation. Subject's own or loaner hearing aid must be optimally fitted using National Acoustics Laboratories' hearing aid fitting formula to confirm eligibility for clinical investigation. (see section 7.3.2.3)
- High Resolution CT imaging: must be completed within 2 years prior to randomisation and show entire cochlea per the imaging protocol. (see section 7.3.1.6)
- Health Survey (HS): must be completed within 90 days prior to randomisation. (see section 7.3.2.1)
- Hearing-Impaired Montreal Cognitive Assessment (HI-MoCA): must be completed within 90 days prior to randomisation. (see section 7.3.2.1)
- Health Utilisation Index III (HUI3): must be completed within 90 days prior to randomisation. (see section 7.3.2.1)
- Dizziness/Tinnitus Questionnaire (DTQ): must be completed within 90 days prior to randomisation. (see section 7.3.2.1)
- Dizziness Handicap Inventory (DHI): must be completed within 90 days prior to randomisation as required by DTQ. (see section 7.3.2.1)
- Tinnitus Handicap Inventory (THI): must be completed within 90 days prior to randomisation as required by DTQ. (see section 7.3.2.1)

7.3.2. Performance/Effectiveness

7.3.2.1. Description of Questionnaires

The following subject facing questionnaires will be completed during the clinical investigation at specified Visits:

- Hearing-Impaired Montreal Cognitive Assessment (HI-MoCA): clinician guided questionnaire that assists in the detection of cognitive impairment. The questionnaire was developed by V. Lin and Sunnybrook Health Sciences Centre (Toronto, Canada).
- Health Survey (HS): clinician guided questionnaire to review for potential inflammatory conditions. The questionnaire was developed by the Sponsor.

The Health Survey (HS) is a clinician guided questionnaire that was developed by the Sponsor to collect health-related data that may be linked to inflammatory conditions that could affect impedance measurements. These include:

- Body temperature
- Blood pressure
- Menstrual cycle phase (if appropriate)
- Relevant medical history, including arthritis, allergies, frequent headaches, other chronic inflammatory conditions [information is captured in the Medical History form]

- Use of antibiotic or anti-inflammatory medication [information captured in the Concomitant Medications Form]
- Other applicable informationHealth Utilities Index III (HUI3): a self-administered questionnaire that includes a rating scale used to measure general health status and health-related quality of life (HRQoL). The questionnaire was developed by Health Utilities Inc.
- Dizziness/Tinnitus Questionnaire (DTQ): clinician guided questionnaire to review dizziness and tinnitus characteristics. The questionnaire was developed by the Sponsor.
- Dizziness Handicap Inventory (DHI): self-administered questionnaire that includes a scale to identify difficulties that you may be experiencing because of dizziness. The questionnaire was developed by Dr. G.P. Jacobson and Dr. C.W. Newman.
- Tinnitus Handicap Inventory (THI): self-administered questionnaire that identifies difficulties that you may be experiencing because of tinnitus. The questionnaire was developed by Dr. C.W. Newman, Dr. G.P. Jacobson, and Dr. J.B. Spitzer.
- Blinding Questionnaire (BQ): self-administered questionnaire to assess subject's understanding of randomisation assignment. The questionnaire was developed by the Sponsor.

7.3.2.2. Description of Audiometric Testing

7.3.2.2.1. Unaided thresholds

Unaided audiometric thresholds will be obtained for each ear independently, using the standard audiometric technique for pure-tone air and bone conduction testing preoperatively to establish candidacy for cochlear implantation and participation in the clinical investigation. Preoperatively, unaided audiometric thresholds will be obtained in both ears. Post-operatively unaided audiometric thresholds will be obtained in the implanted ear to assess the impact of cochlear implantation.

• Air Conduction: 250, 500, 750, 1000, 1500 2000, 3000, 4000, 6000 & 8000 Hz

Hearing thresholds that exceed the air conduction limits of the audiometer, where the participant reports feeling the acoustic stimuli, shall be recorded as vibrotactile (VT). Appropriate masking will be employed where required.

• Bone conduction: 250, 500, 750, 1000, 1500, 2000, 3000 & 4000 Hz

Where the participant reports feeling rather than hearing the acoustic stimuli, the response shall be recorded as vibrotactile (VT). Appropriate masking will be employed where required.

7.3.2.2.2. Aided thresholds: 250, 500, 1000, 2000 & 4000 Hz

Aided audiometric thresholds will be obtained for both ears preoperatively and the implanted ear postoperatively using warble tones. The contralateral ear will be plugged for all tests.

7.3.2.3. Description of Speech Perception Testing

The following speech perception testing will be completed during the clinical investigation:

1. Two lists of CNC words at 60 dBA in quiet delivered from a speaker located directly in front of the listener (S0):

- Screening/Baseline testing scenarios:
 - i. Each ear in the aided condition, with the contralateral ear plugged.
 - ii. Both ears together in the aided condition.
- Post-operative:
 - i. Unilateral: Cochlear implant^p with the contralateral ear plugged.
 - ii. Bimodal: Cochlear implant^p with a hearing aid in contralateral ear.
- 2. One list of AzBio sentences at 60 dBA in guiet delivered from a speaker located directly in front of the listener (SO):
 - Screening/Baseline testing scenarios:
 - i. Each ear in the aided condition, with the contralateral ear plugged.
 - ii. Both ears together in the aided condition.
 - Post-operative:
 - i. Unilateral: Cochlear implant^p with the contralateral ear plugged.
 - ii. Bimodal: Cochlear implant^p with a hearing aid in contralateral ear.

The American AzBio sentences are recorded in Australian and New Zealand accents for use at Australian and New Zealand sites.

In the United States, contralateral hearing aids may be provided to subjects should their own hearing aid not provide optimal therapy.

7.3.2.4. **Description of Battery Life Estimation Test**

Measuring projected sound processor battery life will be completed during the clinical investigation on the ear with CI632/CI632D.

Impedance Measurements 7.3.2.5.

Four point impedance measurements are measured using Custom Sound® EP software or the latest Cochlear software platform for advanced objective measurements. The four point impedance measurement is an investigational measurement and therefore requires a research key in order to activate this measurement in

^p Some individuals will make use of the ipsilateral acoustic component to augment the cochlear implant and as a result allow access to Hybrid stimulation. In these cases, "Cochlear implant" would correspond to Hybrid (i.e., cochlear implant

⁺ hearing aid in the same ear).

Custom Sound EP. FDA reviewed the four point impedance measurement during the IDE review of G200098. The Sponsor may provide a laptop to use this software during the cochlear implant operation and at study visits. A CP910/CP920 sound processor will be used when testing with Custom Sound EP at all study visits.

7.3.2.6. CT Core Lab

Anatomy and cochlear implant electrode placement will be reviewed using high resolution CT of preoperative and post-operative CT scans. Independent review analysis of CT imaging will be completed by a CT corelab.

7.3.2.7. Schedule of Events

A table with a schematic overview of the events is provided in section 3. Please refer to section 3 for details regarding the timing and frequency of the events. In this section more information about the separate events is given.

7.3.2.7.1. Screening and Baseline

Screening and Baseline is described in section 7.3.1

7.3.2.7.2. Randomisation

Randomisation may only be completed once all activities under Screening and Baseline are completed, subject screening/baseline data is entered into the EDC, and eligibility has been confirmed by an independent Sponsor representative.

The ear to be implanted will need to be determined prior to randomization and must be compliant with the inclusion and exclusion criteria. The decision will be made between the investigator, audiologist and subject, and the justification for ear selection must be documented.

7.3.2.7.3. Surgery (day 0)

Data collection from time of Surgery through discharge from hospital includes:

• High Resolution CT: Post insertion to assess electrode placement. Cone beam CT and flat panel CT are examples.

OR

- X-Ray or fluoroscopy (C-arm): required intraoperatively to assess placement of electrode using Modified Stenver's View. X-ray or fluorscopy will be repeated if electrode is repositioned/replaced.
 - If final placement of cochlear implant is not positioned correctly (tip foldover or translocation), the subject will remain in the clinical investigation and complete all assessments. Outcome will be documented in the CRF.
- Electrode Electrical Testing: must be completed intraoperatively after final placement of electrode. If electrode position is altered or second device is used, testing must be repeated. Complete tests in the following order:
 - 1. Impedances (MP1+2 and Four point).
 - 2. AutoNRT[®] (standard 9 electrodes).
- Surgical Questionnaire: surgeon's review of surgical implant.
- Discharge Summary: subject's stay in hospital.

The following requirements are to be followed for the Surgery:

- At the surgeon's discretion, dexamethasone may be utilised in anaesthesia, IV and take-home pack, which will be documented in the CRF.
- Dexamethasone may not be used to treat (e.g. topically) the cochlear implant electrode.
- Dexamethasone may not be used within or near the ear/cochlea.
- Cochlear implant electrode may not be dipped in saline, hyaluronic acid (healon), or other treatment prior to insertion.
- The implant procedure must follow Instructions for Use (IFU). A back up CI632D or CI632 may be required if preparation/insertion is not possible according to IFU.
- Following impedance and/or NRT testing, if the electrode is re-inserted or replaced with a new device, the testing must be repeated

If the IMD or comparator is inserted but not implanted (eg implanted with commercial device), the subject should remain in the clinical investigation for 30 Days or until all AEs are resolved (whichever is longer).

If the IMD or comparator is implanted and then explanted during Surgery or at a later date, the subject should remain in the clinical investigation for 30 Days or until all AEs are resolved (whichever is longer).

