9.5. Analysis Populations

Analyses of endpoints will include the following populations:

- Intent-to-Treat (ITT): all subjects that are randomised. Analysis will be based on randomisation assignment.
- As-Treated (AT): subjects that receive a CI632 or CI632D. Analysis will be based on treatment received (rather than randomisation assignment).
- Per-protocol (PP): subjects that receive a CI632 or CI632D in accordance with randomisation assignment and do not have a translocated electrode as confirmed by imaging.

In addition to these populations, there may be subgroup analysis which could include geography, sex, age or race. The complete analysis strategy will be outlined in the Statistical Analysis Plan (SAP).

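### The 30-day participation rule after a failed or removed device makes no exception for subjects who leave surgery with a back-up CI632D/CI632 or a commercial CI632, so their 6-month data may go uncollected although ITT keeps them

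*Protocol*

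**What the plan says.** Two sentences at the end of Protocol Section 7.3.2.7.3, Surgery (day 0), set a shortened participation period of 30 days or until all adverse events are resolved, whichever is longer:

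- Inserted but not implanted: "If the IMD or comparator is inserted but not implanted (eg implanted with commercial device), the subject should remain" for that period.
- Implanted and then removed: "If the IMD or comparator is implanted and then explanted during Surgery or at a later date, the subject should remain" for that period.

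The same section foresees a second device in the same operation: "A back up CI632D or CI632 may be required if preparation/insertion is not possible according to IFU". It requires electrical testing on that device: "If electrode position is altered or second device is used, testing must be repeated", and again, "if the electrode is re-inserted or replaced with a new device, the testing must be repeated". Neither requirement mentions leaving the study. For tip foldover or translocation, the section states that the subject stays in and completes every assessment.

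Section 7.2.5 counts a subject as implanted if the device received matches the assignment. It makes no condition that this was the first unit opened. A subject who was not successfully implanted, or not implanted as assigned, is a treatment failure, and Section 7.2.6 lists treatment failure as a withdrawal reason. Sections 7.1 and 7.2.6 rule out replacing randomised subjects.

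Section 9.5 defines the main population: "Intent-to-Treat (ITT): all subjects that are randomised. Analysis will be based on randomisation assignment". The As-Treated set takes anyone who received a CI632 or CI632D: "Analysis will be based on treatment received (rather than randomisation assignment"). Section 9.6.1 uses ITT for both 6-month primary endpoints, with multiple imputation left to the SAP.

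**The concern.** A subject whose first device is removed and replaced by a back-up in the same operation meets two provisions of one section. One repeats the tests on the new device, which suggests that follow-up goes on. The other shortens participation to 30 days. A subject randomised to CI632D who ends with a commercial CI632 meets only the second. Section 8.5 says the CI600 series is commercially available, so this case is possible.

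If a site applies the shortened period, Visit 5 is never held. The subject still counts in ITT, cannot be replaced and may belong to the As-Treated set, but has no 6-month MP1+2 impedance. A subject randomised to CI632D may also have no 6-month CNC score. These values could have been measured at a visit already in the schedule.

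The trigger is a surgical event after randomisation, and the surgeon knows the arm (Sections 7.1.1 and 7.2.7.1). Section 4.3 links insertion trauma to inflammation and fibrosis, and impedance to fibrotic tissue. Subjects who needed a second device may therefore differ on the primary outcome, so the missingness could be informative.

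**Working it through.** **1. What happens to each type of subject**

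| Situation | Shortened-participation sentences | Other text |
|---|---|---|
| Device fails in preparation and is never inserted; back-up used | Neither applies | Implanted if of the assigned type; continues |
| Device implanted, removed in the same operation; back-up of assigned type implanted | Second sentence applies literally | Testing repeated; implanted under 7.2.5; suggests continuation |
| CI632D inserted but not implanted; commercial CI632 implanted | First sentence applies | Treatment failure under 7.2.5; ITT by assignment; As-Treated as CI632 |
| Tip foldover or translocation | Neither applies | Stays in, all assessments |

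The second row is contradictory. The third points to departure at about 30 days, although both analysis sets have a use for the 6-month impedance.

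**2. The plan's own sample size**

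Inputs from Section 9.4: difference 1.5 kOhm, SD 2.0 kOhm, one-sided alpha 0.025, power 0.9, 1:1 allocation. For a two-sample t-test with n per arm, the noncentrality is 1.5 / (2.0 × √(2/n)) on 2n − 2 degrees of freedom.

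- n = 38: power 0.897.
- n = 39: power 0.905.

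The stated 39 per arm reproduces.

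**3. Effect on power**

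The documents give no rate of back-up, commercial-device or explant cases. I assume 0% to 10% early exits on top of the plan's 10% attrition, with a fixed-sample test.

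- 50 per arm: 50 × 0.90 = 45 evaluable, power 0.940. With 10% exits, 50 × 0.80 = 40, power 0.912.
- 60 per arm: 60 × 0.90 = 54 evaluable, power 0.971. With 10% exits, 60 × 0.80 = 48, power 0.953.

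**4. Effect on type I error**

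Assumptions, none of them from the documents: 2% or 5% of one arm is lost through the rule, their true impedance is 2 kOhm above the arm mean, and they are imputed at the arm mean. In an arm of 60, that is 60 × 0.02 = 1.2 to 60 × 0.05 = 3 subjects.

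- Shift in that arm's mean: 0.05 × 2 = 0.10 kOhm, or 0.02 × 2 = 0.04 kOhm. The larger is 0.10 / 1.5 = 7% of the target difference.
- Standard error at 54 per arm: 2.0 × √(2/54) = 0.385 kOhm. A 0.10 kOhm shift is 0.10 / 0.385 = 0.26 standard errors.

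Probability of rejecting at one-sided 0.025 when the true difference is zero (noncentral t, 106 degrees of freedom):

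| Loss pattern | Shift favouring CI632D (kOhm) | Type I error |
|---|---|---|
| 5% from control only | −0.10 | 1.3% |
| 2% from control only | −0.04 | 2.0% |
| Equal loss in both arms | 0 | 2.5% |
| 2% from CI632D only | +0.04 | 3.2% |
| 5% from CI632D only | +0.10 | 4.4% |

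These are fixed-sample figures and ignore the group sequential boundaries.

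**The case against.** The strongest reply is that the protocol never says a back-up recipient leaves. The IMD or comparator can mean the device type rather than the first unit. Section 7.2.5 fits that reading, and so does the repeat testing. The rule also speaks of how long a subject should remain, with the longer of two periods, so departure is implied rather than stated. This stands for a back-up of the assigned type: it is an ambiguity, not a written exit rule. It helps less for a commercial CI632 after assignment to CI632D, where the treatment-failure status and its listing as a withdrawal reason point to departure.

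A reader might go further in three ways that the documents do not support.

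- **Both primary endpoints are lost for every affected subject.** Endpoint 2 analyses only subjects randomised to CI632D for whom CI632D is the first cochlear implant (Section 9.6.1). Control subjects lose only impedance, and a subject who ends with a commercial CI632 may fall outside that cohort. There is also no commercial CI632D, because the synopsis describes it as premarket.
- **Imputation would draw only on smooth insertions.** Malpositioned arrays stay in with full assessment and re-inserted electrodes are retested, so difficult insertions are among the observed data. The imputation model belongs to the SAP.
- **Type I error is inflated to 4.4%.** That is one assumed corner. Equal loss gives no inflation and loss from control alone is conservative. Sections 5.1.6 and 8.4 describe the same surgery and handling for both devices, so unequal loss rests mainly on the unblinded surgeon.

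The As-Treated set is also only modest evidence of conflict: it could serve allocation errors, and its use for the primary endpoints is optional.

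**Conclusion.** The point holds as a gap in the follow-up rule that should be closed. On its literal wording, the rule can end participation before Visit 5 for subjects who carry a CI632 or CI632D, stay in the primary ITT analysis and cannot be replaced. Other text in the same protocol points the other way for a back-up of the assigned type, and sites could apply either reading.

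The consequence is avoidable and possibly informative missing impedance at 6 months and, for some subjects randomised to CI632D, a missing CNC score. Under the assumptions stated (2% to 5% lost from one arm, 2 kOhm excess, imputed at the arm mean), one-sided type I error ranges from about 1.3% to 4.4%, with 2.5% under equal loss. The direction is unknown. Power at 50 or 60 per arm stays above 0.90 even with 10% extra exits, so the matter is ITT completeness and possible bias. No sample size figure is wrong on this point. Values missed at 6 months cannot be recovered later.

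**What to change.** Reconcile Sections 7.2.5, 7.3.2.7.3, 9.5 and 9.6.1 with one added sentence. State that the 30-day period is a minimum safety follow-up, and that it ends participation only when the subject has neither a CI632 nor a CI632D in place. A randomised subject who leaves surgery with either device, whether the first unit, a back-up or a commercial CI632, stays on the existing visit schedule for data collection. Visit 5 data are analysed by randomised arm in ITT and, where that set is used, by device received in As-Treated. Section 9.6.1 should say whether a subject randomised to CI632D who ends with a CI632 belongs to the endpoint 2 cohort.

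This changes data collection only. The cost is a short amendment and a few subjects attending visits that are already scheduled.
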